5.2 Exclusion Criteria

An individual who meets any of the following criteria will be excluded from participation in this study:

1. Does not provide informed consent.

5.3 Vulnerable Subjects

No vulnerable populations will be enrolled.

5.4 Strategies for Recruitment and Retention

OnTrack staff inform family members about the study using the recruitment script and recruitment flyer which will be distributed as physical flyers and through the OTNY listserv along with study description. If interested, secure a document with their contact information and their agreement to be contacted by a member of the research team. Potentially eligible participant information will be forwarded to a member of the research team, who will provide greater detail about the study, determine eligibility, and answer any questions the potential participant may have. If the potential participant meets the eligibility criteria and is interested in participating, the research staff will review the consent form with the participant and secure informed consent via REDCap. The participant will complete the baseline assessment by phone.

Retention will be enhanced via gathering multiple phone numbers and having regular contact. Further, to

improve enrollment and retention, we will explain to potential subjects that everybody will at some point be eligible to get a Family Connector. Participants in the control group will have access to receive a Family Connector after the completion of their T3 assessment.

For the qualitative interviews with our Family Connectors, Family Connectors will be informed about the study during their weekly check-in with the research team. If interested in participating, the research staff will review the consent form with the Family Connector, titled the “Family Connectors Consent Form,” and secure informed consent via REDCap. The participant will complete the interview by zoom.

For the qualitative interviews with family members, a member of the research team will contact every participant who worked with a Family Connector. If interested in participating, the research staff will review the consent form with the participant and secure informed consent via REDCap. They will be informed that the interview will be used to create a transcript and will choose whether or not they feel comfortable having the interview recorded. The participant will also have the choice to complete the interview either by Zoom or phone call.

5.5 Duration of Study Participation

Participants will be enrolled for approximately nine months post-study initiation (baseline to posttest), and up to 15 months if they are in the waitlist condition and choose to work with a Family Connector after the completion of T3.

The qualitative interview with our Family Connectors will take up to one hour.

The qualitative interview with family members will take up to one hour.

5.6 Total Number of Participants and Sites

We will aim for a total sample of 96 participants.

5.7 Participant Withdrawal or Termination

Participants are free to withdraw from participation in the study at any time upon request. An investigator may terminate participation in the study if:

- Any clinical adverse event (AE), laboratory abnormality, or other medical condition or situation occurs such that continued participation in the study would not be in the best interest of the participant
- The participant meets an exclusion criterion (either newly developed or not previously recognized) that precludes further study participation

5.7.2 Handling of Participant Withdrawals or Termination

If subjects decline at any time point, they will be considered withdrawn from the study and will no longer be contacted for the remainder of the study.

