4.1 Description of Study Design

The study will employ a randomized controlled study design; a total of 96 family members who participated in OnTrack with their adolescent/young adult will be randomized to either Family Connectors or a waitlist comparison group. Data will be collected at baseline (upon the discharge of the adolescent/young adult from OTNY), a follow up (one-month post-baseline) and posttest (seven months post-baseline). For participants in the waitlist condition who choose to work with a Family Connector after their posttest, an identical posttest will be collected at the end of their 6-month intervention period. Both conditions will receive a packet of community resources.

We will conduct a single qualitative interview with each of the Family Connectors to get feedback on their experience as a Family Connector and receive suggestions for further modifications and improvements that can be made to the Family Connectors model.

5 Study Enrollment and Withdrawal

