6.2 Intermediate Visits

Weekly phone calls by a Family Connector for between three and six months.

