6.4 Withdrawal Visit

If subject withdraws early or investigator terminates subject participation, the subject will no longer be contacted.

7 Study Procedures/Evaluations

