7.1 Questionnaire Administration

Study measures include one questionnaire that taps into the following domains: (1) sociodemographic characteristics of the family member, (2) family member perceived self-efficacy, (3) family member/caregiver social support, caregiver strain, satisfaction with Family Connectors, and (4) the adolescent/young adult's functioning at school and work. The questionnaire will be collected via REDCap at three time points (with the exception of the sociodemographic questionnaire, which will be collected at T1 only, and satisfaction questions, which will be collected at T3 and T4 only).

See the Appendix for a copy of the measures.

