7.2 Procedures/Evaluations

The measure will be administered at baseline (upon discharge from OTNY), one-month post-baseline (prior to intervention) and posttest (following the conclusion of the intervention). *For participants in the waitlist condition who choose to work with a Family Connector after their posttest, an identical posttest will be collected at the end of their 6-month intervention period.*

See the Appendix for a copy of the measure.

8 Safety and Adverse Events

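### Section 5.7.2 does not say what is declined; applied to one refused assessment, it gives up T3 from people who might still answer

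*Combined protocol and SAP*

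**What the plan says.** **The rule.** Section 5.7.2: "If subjects decline at any time point, they will be considered withdrawn from the study and will no longer be contacted". Section 6.4 has a different trigger: "If subject withdraws early or investigator terminates subject participation, the subject will no longer be contacted". It does not use the word *decline*. Section 5.7 already covers leaving on request: "Participants are free to withdraw from participation in the study at any time upon request". Section 2.3.1 lets participants leave individual questions unanswered.

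**The assessments.** Section 7.1: "The questionnaire will be collected via REDCap at three time points". Section 14.3 likewise pays a gift card per timepoint. Section 7.2 places the assessments after baseline at "one-month post-baseline (prior to intervention) and posttest (following the conclusion of the intervention". Section 4.1 puts the posttest (T3) seven months after baseline.

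**After T3.** Section 5.4: "Participants in the control group will have access to receive a Family Connector after the completion of their T3 assessment". The later questionnaire is for a self-selected part of one arm (4.1): "For participants in the waitlist condition who choose to work with a Family Connector after their posttest, an identical posttest will be collected".

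**Size and analysis.** Section 3.1 assigns 48 family members to each arm. Section 10.2 bases the 96 on expected recruitment. It gives no effect size, alpha, power or dropout allowance. Section 10.3 gives no missing-data method.

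**The concern.** Three different events could be called declining: refusing one questionnaire, stopping the calls, and leaving the study. Only the last is clearly a request for no more contact. Section 5.7.2 attaches the same consequence to declining without saying which event it means, so staff could apply it differently from one participant to the next.

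The case that matters is a refusal at T2. That assessment comes before the intervention and carries no information on its effect. If one refusal there ends contact, T3 is lost too, and no later assessment can replace it as a randomised comparison. The retention steps in 5.4 cannot recover a person whom the rule bars from contact, and neither 10.2 nor 10.3 makes any allowance for the loss. At stake is the precision of the one comparison that can test the hypotheses in 10.1 as effects of the programme.

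**Working it through.** **1. Which assessment carries the randomised comparison?**

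| Assessment | Timing | After the intervention? | Both arms as randomised? |
|---|---|---|---|
| T1 | baseline | no | yes |
| T2 | one month | no | yes |
| T3 | seven months | yes | yes |
| T4 | after the waitlist arm's own intervention period | yes | no, only waitlist participants who choose it |

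Only T3 qualifies on both counts.

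**2. Whom does the rule cost?** On the broad reading, it costs only people who decline T2 and would still have answered T3. Someone who declines T3 itself is lost under any rule. The relevant rate is therefore refusal at T2, not total loss to follow-up.

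**3. Inputs.** From the documents: 48 per arm (3.1). The plan has no power figure to reproduce, because 10.2 is a recruitment forecast. Assumed: standardised difference d = 0.5; two-sided 5% t-test; T2 refusal p of 5%, 10% or 20%, equal in both arms; share r of T2 decliners who would complete T3 if invited, 25% to 75%; no other loss.

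**4. Formulas.**
- Number per arm at T3 under the rule: 48(1 − p).
- Number per arm if decliners are still invited: 48(1 − p + rp).
- T3 records forfeited over both arms: 96pr.
- Power from the noncentral t distribution with 2n − 2 degrees of freedom and noncentrality d√(n/2), n not rounded.

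**5. Results.** With all 48 per arm, power is 67.9%.

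| p | n per arm under the rule | Power under the rule | Power if invited (r = 25%, 50%, 75%) | Cost of the rule, points | T3 records forfeited |
|---|---|---|---|---|---|
| 5% | 45.6 | 65.6% | 66.2%, 66.8%, 67.3% | 0.6, 1.2, 1.7 | 1.2, 2.4, 3.6 |
| 10% | 43.2 | 63.2% | 64.4%, 65.6%, 66.8% | 1.2, 2.4, 3.6 | 2.4, 4.8, 7.2 |
| 20% | 38.4 | 58.0% | 60.7%, 63.2%, 65.6% | 2.7, 5.2, 7.6 | 4.8, 9.6, 14.4 |

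Example: at p = 10% and r = 50%, n rises from 48 × 0.90 = 43.2 to 48 × 0.95 = 45.6, and 96 × 0.10 × 0.50 = 4.8 records are kept. If r = 0, or on the narrow reading, the rule costs nothing.

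**6. Bias.** If a share p of an arm is lost and those lost differ from those observed by g, the arm's observed mean is off by pg. The arm difference is off by p₁g₁ − p₀g₀. This is zero when refusal and gap are the same in both arms. The documents give neither quantity.

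**7. The adverse-event passages.** Section 5.7 lets the investigator end participation because of an adverse event, and 6.4 then ends contact. Section 8.1 has the investigator follow unresolved events until they resolve, are explained, or the subject is lost to follow-up. Section 8.2 requires each event's course to be followed to resolution, stabilisation or a finding that the study is not the cause. The conflict does not depend on what *decline* means.

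**The case against.** The strongest answer is that the natural reading is harmless. Section 5.7.2 stands under a heading on withdrawals and termination and follows the right to withdraw in 5.7. Section 6.4, the parallel rule, speaks of withdrawing early. *At any time point* may mean no more than *at any time*. Section 2.3.1 shows that not every refusal counts as withdrawal. On this reading, ending contact simply respects the request. The consent form is not in the text reviewed, and the manual of procedures mentioned in 13.3 may also define withdrawal.

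Much of this stands: the narrow reading is available and costs nothing. It does not settle the matter, because 5.7.2 makes withdrawal the consequence of declining rather than its meaning, and 7.1 and 14.3 use the same term for assessments. No section says what follows one refused questionnaire.

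A reader might go further in three ways that the documents do not support.
- **That stopping the calls triggers the rule.** The text does not say so, and shorter participation can be planned: "Weekly phone calls by a Family Connector for between three and six months".
- **That the rule biases the result.** This needs refusal, or the gap between decliners and completers, to differ by arm. Since T2 precedes the intervention, nothing in the plan points to such a difference there. Loss from refused calls could fall on one arm, but that rests on the weaker reading above.
- **That all dropout is due to the rule.** Only refusal at T2 by people still willing at T3 is.

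**Conclusion.** The point holds as a conditional one. The wording of 5.7.2 permits a reading under which one refusal at T2 forfeits the only randomised post-intervention outcome. On that reading, with the assumed d = 0.5 and 25% to 75% of T2 decliners still willing, the cost is about 0.6 to 1.7 points of power at 5% T2 refusal and 2.7 to 7.6 at 20%. If T2 refusal is low, the loss is small. On the narrow reading it is zero. None of these rates comes from the documents. Bias is possible, but neither its size nor its direction can be derived. The change is worth making because it is cheap and T3 answers cannot be collected later on the same footing. The conflict between 6.4 and sections 8.1 and 8.2 stands on any reading.

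**What to change.** In 5.7.2:
- State that a participant who declines an assessment or stops the calls is still invited to every remaining assessment, including T3, unless they ask to leave the study or withdraw consent to be contacted.
- State that data already collected are used, consistent with 12.4.
- State that loss will be reported by arm, with reasons.

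Align the wording of 6.4 with this. Separately, reconcile its no-contact rule for investigator-terminated subjects with the adverse-event follow-up in 8.1 and 8.2.

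The cost is a protocol amendment approved by the IRB, with a decision on re-consent (12.2), a few more invitations to people who declined once, and the $50 payments already planned per timepoint (14.3). Anyone who asks for no further contact is still left alone.

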5.7.3 Premature Termination or Suspension of Study

This study may be temporarily suspended or prematurely terminated if there is sufficient reasonable cause. Written notification, documenting the reason for study suspension or termination, will be provided

by the suspending or terminating party to NYU. If the study is prematurely terminated or suspended, the PI will promptly inform the IRB and will provide the reason(s) for the termination or suspension. Circumstances that may warrant termination or suspension include, but are not limited to:

- Determination of unexpected, significant, or unacceptable risk to participants
- Demonstration of efficacy that would warrant stopping
- Insufficient compliance to protocol requirements
- Data that are not sufficiently complete and/or evaluable
- Determination of futility

Study may resume once concerns about safety, protocol compliance, data quality are addressed and satisfy the sponsor and/or IRB.

6 Study Schedule

6.1 Enrollment/Baseline

Enrollment/Baseline Visit 1

- Verify eligibility
- Obtain signed informed consent from participants (see the Appendix).
- Collect baseline assessment

Procedures listed are consistent with those included in the Schedule of Events (Appendix A).

6.2 Intermediate Visits

Weekly phone calls by a Family Connector for between three and six months.

6.3 Final Study Visit

Final Study Visit 2

- Complete posttest assessment

Procedures listed are consistent with those included in the Schedule of Events (Appendix A).

6.4 Withdrawal Visit

If subject withdraws early or investigator terminates subject participation, the subject will no longer be contacted.

7 Study Procedures/Evaluations

7.1 Questionnaire Administration

Study measures include one questionnaire that taps into the following domains: (1) sociodemographic characteristics of the family member, (2) family member perceived self-efficacy, (3) family member/caregiver social support, caregiver strain, satisfaction with Family Connectors, and (4) the adolescent/young adult's functioning at school and work. The questionnaire will be collected via REDCap at three time points (with the exception of the sociodemographic questionnaire, which will be collected at T1 only, and satisfaction questions, which will be collected at T3 and T4 only).

See the Appendix for a copy of the measures.

7.2 Procedures/Evaluations

The measure will be administered at baseline (upon discharge from OTNY), one-month post-baseline (prior to intervention) and posttest (following the conclusion of the intervention). *For participants in the waitlist condition who choose to work with a Family Connector after their posttest, an identical posttest will be collected at the end of their 6-month intervention period.*

See the Appendix for a copy of the measure.

8 Safety and Adverse Events

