12.2	INSTITUTIONAL REVIEW BOARD.....	12
12.3	INFORMED CONSENT PROCESS	13
12.3.1	Consent/Assent and Other Informational Documents Provided to Participants	13
12.3.2	Consent Procedures and Documentation.....	13
12.4	PARTICIPANT AND DATA CONFIDENTIALITY	13
13	DATA HANDLING AND RECORD KEEPING.....	14
13.1	DATA COLLECTION AND MANAGEMENT RESPONSIBILITIES	14
13.2	STUDY RECORDS RETENTION	15
13.3	PROTOCOL DEVIATIONS	15
13.4	PUBLICATION AND DATA SHARING POLICY	15
14	STUDY FINANCES	15
14.1	FUNDING SOURCE.....	15
14.2	COSTS TO THE PARTICIPANT.....	15
14.3	PARTICIPANT REIMBURSEMENTS OR PAYMENTS	15
15	STUDY ADMINISTRATION	16
15.1	STUDY LEADERSHIP	16
16	CONFLICT OF INTEREST POLICY	16
17	ATTACHMENTS	17

[figure not shown]
List of Abbreviations

AE	Adverse Event/Adverse Experience
CFR	Code of Federal Regulations
CRF	Case Report Form
DCC	Data Coordinating Center
FFR	Federal Financial Report
HIPAA	Health Insurance Portability and Accountability Act
IRB	Institutional Review Board
MOP	Manual of Procedures
N	Number (typically refers to participants)
NIH	National Institutes of Health
NYC H+H	New York City Health + Hospitals
OHRP	Office for Human Research Protections
PI	Principal Investigator
QI	Quality Improvement
SAE	Serious Adverse Event/Serious Adverse Experience
US	United States

Protocol Summary

Title	Examining the Impact of Family Connectors
Short Title	Family Connectors
Brief Summary	This study will examine the impact of Family Connectors amongst 96 family members of adolescents/young adults with first episode psychosis who were discharged from OnTrack.
Objectives	The study objectives are to examine the association between involvement in Family Connectors, a manualized peer-to-peer support and education program for family members of adolescents or young adults with symptoms of first episode psychosis, and feelings of empowerment, self-efficacy and social support. A total of 96 family members will be enrolled in this study, and will be enrolled in either Family Connectors + a packet of community resources or the community resource alone. Outcomes consist of the family member's feelings of self-efficacy, connection to services and supports, caregiving strain, satisfaction, and perceptions of adolescent/young adult functional outcomes at school and work.
Methodology	RCT with data collection and baseline (T1), follow-up (one-month post-baseline, T2) and posttest (six months past T2xx).

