Endpoint	The primary endpoint of the study is when data collection is completed for 96 participants.
Study Duration	Approximately 2 years.
Participant Duration	Approximately 9 months from enrollment to completion of posttest data.
Population	96 adults who are (1) English speaking, (2) 18 years of age or older, (3) a family member of an adolescent/young adult with first episode psychosis who was discharged from OnTrack.
Study Sites	The participating site is the NYU Langone School of Medicine and Washington University.
Number of participants	96 family members will be enrolled at NYU Langone School of Medicine
Statistical Analysis	Descriptive analyses will be conducted to calculate means and standard deviations for continuous data and numbers and percentages for dichotomous data. Bivariate and multivariate analyses will examine between and within group differences from baseline to posttest.

Schematic of Study Design

1 Key Roles

[name], [name] Professor of Child and Adolescent Psychiatry
NYU Grossman School of Medicine
[name]
[name]
[contact]
Email: [contact]

[name]
Research Associate
NYU Grossman School of Medicine
[name]
[name]
[contact]
Email: [contact]

[name]
Project Coordinator/Parent Partner
NYU Grossman School of Medicine
[name]
[name]
[contact]
Email: [contact]

[name].
Project Consultant
Clinical Professor
Herbert Wertheim School of Public Health and Longevity Science
University of California, San Diego
[name]
[name]
[contact]
Email: [contact]

[name]
Research Associate
NYU Grossman School of Medicine
[name]
[name]
[contact]
Email: [contact]

[name]
Associate Research Scientist
NYU Grossman School of Medicine
[name]
[name]
[contact]
Email: [contact]

[name]
Project Coordinator
NYU Grossman School of Medicine
[name]
[name]
[contact]
Email: [contact]

2 Introduction, Background Information and Scientific Rationale

2.1 *Background Information and Relevant Literature*

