10.3 Statistical Methods

Univariate statistics will be employed to describe the sample characteristics. Categorical data will be presented in percentages; interval and ratio-level data will be presented via measures of central tendency and dispersion (e.g., means, standard deviations). Bivariate and multivariate analyses will be conducted in order to examine between and within group differences in outcomes.

11 Source Documents and Access to Source Data/Documents

Source data is all information, original records of clinical findings, observations, or other activities in a study necessary for the reconstruction and evaluation of the study. Source data are contained in source documents. Examples of these original documents, and data records include: hospital records, clinical and office charts, laboratory notes, memoranda, subjects' diaries or evaluation checklists, pharmacy dispensing records, recorded data from automated instruments, copies or transcriptions certified after verification as being accurate and complete, microfiches, photographic negatives, microfilm or magnetic media, x-rays, subject files, and records kept at the pharmacy, at the laboratories, and at medico-technical departments involved in the study.

The study case report form (CRF) is the primary data collection instrument for the study. All data requested on the CRF must be recorded. All missing data must be explained. If a space on the CRF is left blank because the procedure was not done or the question was not asked, write "N/D". If the item is not applicable to the individual case, write "N/A". All entries should be printed legibly in black ink. If any entry error has been made, to correct such an error, draw a single straight line through the incorrect entry and enter the correct data above it. All such changes must be initialed and dated. DO NOT ERASE OR WHITE OUT ERRORS. For clarification of illegible or uncertain entries, print the clarification above the item, then initial and date it.

Access to study records will be limited to IRB-approved members of the study team. The investigator will permit study-related monitoring, audits, and inspections by the IRB/EC, the sponsor, government regulatory bodies, and University compliance and quality assurance groups of all study related documents (e.g. source documents, regulatory documents, data collection instruments, study data etc.). The investigator will ensure the capability for inspections of applicable study-related facilities.

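### The one-month assessment (T2) is taken before the intervention, but the plan gives it no coherent role: the hypotheses treat it as an outcome time and the analysis section assigns it nothing

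*Combined protocol and SAP*

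**What the plan says.** **Timing.** Section 7.2 gives the second assessment as "one-month post-baseline (prior to intervention", without restricting this to one arm. The Protocol Summary (Methodology) lists "follow-up (one-month post-baseline, T2) and posttest (six months past T2xx", and Section 4.1 has "a follow up (one-month post-baseline) and posttest (seven months post-baseline". Section 6.2 describes the intervention as "Weekly phone calls by a Family Connector for between three and six months".

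**Content.** Section 7.1 states: "The questionnaire will be collected via REDCap at three time points". It excepts only sociodemographics (T1 only) and satisfaction (T3 and T4 only), so the outcome scales are collected at T2. Attachment A also schedules an assessment at T1, T2 and T3.

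**Analysis.** The Protocol Summary says the analyses "will examine between and within group differences from baseline to posttest". Section 10.3 says: "Bivariate and multivariate analyses will be conducted in order to examine between and within group differences in outcomes". It names no time point, model or covariate.

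**Hypotheses.** Hypotheses 1 and 2 in Section 10.1 each expect better outcomes at two times, post-test and follow-up.

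**The concern.** Three parts of the protocol point T2 in different directions. Section 7.2 makes it a second pre-intervention reading. Section 10.1, read with the protocol's own labels, makes it a time at which benefit is expected. The analysis text gives it no role.

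Two things are at stake:

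- **The hypotheses.** As written, half of each one would be tested on data collected before the intervention, where no effect of the calls is possible. A null result there would say nothing about the programme. An arm difference there would have to come from chance, or from families knowing their assignment.
- **Precision.** A second pre-intervention reading of the same scale can sharpen the T3 comparison at no cost in data. The sample of 96 was not derived from a power calculation, and T2 is already paid for: Section 14.3 gives $50 per time point, so up to 96 × $50 = $4,800. If its use is not fixed in advance, the choice will be made after the data are seen.

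**Working it through.** **1. Is T2 really before the intervention?** The Summary puts posttest six months after T2, and Section 4.1 puts it seven months after baseline. Since 1 + 6 = 7, these agree. The window from T2 to T3 is 7 − 1 = 6 months, which holds three to six months of calls. The calendar therefore supports Section 7.2.

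**2. What does follow-up in Section 10.1 refer to?** The Summary and Section 4.1 both attach that label to the one-month assessment. The word order in 10.1 might suggest something later than posttest, but Attachment A has nothing after T3. The only later assessment is the repeat posttest for waitlist families who choose to take up a Family Connector (Sections 4.1 and 7.2), and that gives no comparison between arms. Sections 10.1 and 7.2 therefore conflict.

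**3. The plan's own figure.** Section 3.1 gives 48 + 48 = 96. Section 10.2 bases 96 on about 150 families a year, and 96/150 = 64%. No alpha, power, effect size, SD or dropout is stated, so there is no power figure to reproduce.

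**4. What T2 could add to a T1-adjusted comparison at T3.** The documents give no correlations, so all of those below are assumed. With outcome SD = 1 and correlations r12 (T1–T2), r13 (T1–T3) and r23 (T2–T3):

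- Residual variance adjusting for T1: V1 = 1 − r13².
- Adjusting for T1 and T2: V2 = 1 − (r13² + r23² − 2·r12·r13·r23)/(1 − r12²). With all three equal to ρ, this is 1 − 2ρ²/(1 + ρ).
- Variance reduction = 1 − V2/V1. Equivalent sample = 96 × V1/V2.

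Example with all at 0.5: V1 = 1 − 0.25 = 0.750, V2 = 1 − 0.5/1.5 = 0.667, and the reduction is 1 − 0.667/0.750 = 11.1%.

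| r12 | r13 | r23 | V1 | V2 | Reduction | Equivalent N |
|---|---|---|---|---|---|---|
| 0.4 | 0.4 | 0.4 | 0.840 | 0.771 | 8.2% | 104.5 |
| 0.5 | 0.5 | 0.5 | 0.750 | 0.667 | 11.1% | 108.0 |
| 0.6 | 0.6 | 0.6 | 0.640 | 0.550 | 14.1% | 111.7 |
| 0.7 | 0.7 | 0.7 | 0.510 | 0.424 | 17.0% | 115.6 |
| 0.7 | 0.5 | 0.55 | 0.750 | 0.672 | 10.5% | 107.2 |
| 0.8 | 0.5 | 0.5 | 0.750 | 0.722 | 3.7% | 99.7 |
| 0.9 | 0.5 | 0.5 | 0.750 | 0.737 | 1.8% | 97.7 |

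In terms of power, assume an effect of 0.5 SD, two-sided 5%, 48 per arm and no dropout, so that power = Φ(0.5/√(2V/48) − 1.96). With r13 = 0.5, T1 adjustment alone gives 80.7%. Adding T2 gives 85.1% (all correlations 0.5), 82.2% (r12 = 0.8, r23 = 0.5) or 81.4% (r12 = 0.9, r23 = 0.5).

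**5. The condition.** These gains require that T2 cannot have been affected by assignment. The protocol does not say whether randomisation, or telling families their arm, comes before or after T2. The comparison group is a waitlist and no blinding is described, so a family that knows its arm could answer self-report scales differently at T2. In that case T2 is not a safe covariate. A model that gives T2 its own arm means leaves the T3 estimate unchanged for complete data and helps only where T3 is missing.

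**The case against.** The strongest reply is that no passage drops T2. A reader might infer from the Summary that the analysis uses baseline and posttest only and throws the T2 data away. The documents do not support that. The Summary line is one sentence whose span can include T2, Section 10.3 is silent, and Section 10.1 does name follow-up. The defect is an undefined and contradictory role, not a stated exclusion.

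Three further points carry weight:

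- **Size.** Equal correlations favour T2. With assessments 1 and 6 months apart, T1–T2 would ordinarily be the highest correlation, which pushes the gain towards the low rows of the table. The formulas also ignore the cost of estimating one more coefficient, which would take part of a 2% gain.
- **Comparator.** The plan does not specify adjustment for T1 either, so both sides of the calculation are assumed models. Against a plain change from T1, averaging T1 and T2 would cut the variance by 25% under equal correlation (1.5(1 − ρ) against 2(1 − ρ)), but the plan does not commit to change scores.
- **Nature.** Using a second pre-treatment reading is a matter of efficiency. Leaving it out would not bias the T3 comparison.

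The conflict between 10.1 and 7.2 and the unstated order of randomisation and T2 remain after all of this.

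**Conclusion.** The point holds in a limited form. T2 is described as pre-intervention in both arms and carries the outcome scales, but the hypotheses name it as a time of benefit and the analysis text assigns it no role. The conflict in the hypotheses needs correcting whatever is decided about precision.

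Where T2 comes before randomisation, or at least before disclosure of assignment, adding it to T1 reduces the variance of the T3 comparison by about 2% to 17%: 8% to 17% if all three correlations are equal at 0.4 to 0.7, and about 2% to 4% if T1–T2 is 0.8 to 0.9 and both others are 0.5. These figures rest on assumed correlations, continuous scores and complete data. Where assignment is known before T2, they do not apply.

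A reader might also infer that T2 must predict T3 better than T1 does, because T1 falls at discharge. Nothing in the documents shows that discharge distorts the T1 scores, so this is not relied on.

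**What to change.** 1. **Section 10.1.** Reconcile with Section 7.2, so that T3 (posttest) is the time at which the intervention effect is tested.
2. **Section 4.1.** State when randomisation takes place, and when families learn their assignment, relative to T2.
3. **Section 10.3.** Estimate the arm difference at T3 adjusting for the T1 value of the same outcome. Where T2 comes before randomisation, or at least before disclosure, also use T2, either as a second covariate or in one longitudinal model of T1, T2 and T3 with common arm means before the intervention.
4. **Section 10.3, alternative.** If assignment is known before T2, keep T2 out of the covariates. Use it only as a repeated response with its own arm means, or in handling missing T3.

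The cost is a few sentences across three sections, settled before the data are analysed, and needs no new data, visits or payments.
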